¹⁰ If CSF sample is positive for abnormal cells or outside reference ranges for any of the following: 1. total protein 2. glucose 3. cell count, it must be repeated within 4 weeks of the sample at screening. If abnormal CSF glucose (CTCAE \geq Grade 2) is obtained, a fasting serum glucose is to be obtained at next patient visit. At week 26, the CSF analysis should include cytology only.

¹¹ Treatment with potassium iodide and Cytomel should be initiated 1 week prior to each ¹³¹I- omburtamab infusion in a cycle and continue until 2 weeks after ¹³¹I- omburtamab infusion in the same cycle..

¹² Thyroid protection should be initiated 1 week prior to IMP administration. See section 7.2.5 for further details.

¹³ Thyroid protection should be initiated 1 week prior to next IMP administration – this is only applicable for week 4 and not week 8. See section 7.2.5 for further details.

¹⁴ Beginning 24 hours before ¹³¹I-omburtamab administration please see section 6.1.2.

¹⁵ Given 1-2 hours prior to ¹³¹I-omburtamab administration, including oral acetaminophen/paracetamol and antihistamine (e.g., diphenhydramine), please see section 6.1.2¹⁶
Drawn and held for culture if elevated body temperature after dosing suggests infection rather than expected response to intracerebroventricular dosing.

¹⁷ Dose reduction: 50% (25 mCi) for patients < 1 of age and 33% (33.5 mCi) for patients age 1 year to < 3 years of age, respectively.

¹⁸ Non-SAE's captured from signing the informed consent form (ICF) to dosing should be recorded as medical history. AEs should be reported until 3 weeks after the last IMP administration. SAE's should be captured from signing the ICF. Starting at week 4 (for patients receiving only one cycle) and starting at week 8 (for patients receiving both cycles) only SAEs considered related to ¹³¹I-omburtamab or new onset of cancers regardless of causality should be reported.

¹⁹ Limit to therapy related to cancer.

²⁰ In case fertile women (experienced menarche prior to screening or during treatment, until week 8) are enrolled; pregnancy testing should take place at screening, at week 4 and week 8, and at follow-up at week 26.

²¹ Follow-up at week 26 (24-29 weeks after first treatment) and Long-term follow-up visits at Weeks 52, 78, 104, 130 & 156 (\pm 4 weeks) can be done at referral site.

²² If done at referral site imaging parameters as required in the Imaging Manual should be followed to the extent possible.

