The median survival for the patients included in the interim analysis was 47 months versus 6 months in various historical cohorts (Kramer, Kushner, and Modak 2017; Berthold, Hömberg, and Baadsgaard 2017). Survival past 3 years historically is rare, less than 10% (Kramer et al. 2017), which is aligned with findings by (Berthold, Hömberg, and Baadsgaard 2017), demonstrating a 3-year survival rate of 8.2% (Berthold et al. 2017). In contrast, for NB patients in study 03-133, the estimated 3-year survival of 56% and an estimated 5-year survival of 43% is reported. Survivors have been followed for up to 11.1 years, with a current mean duration of follow up of 2.6 years. Fifty-one (54.8%) of the █ patients treated with ^{131}I -omburtamab remained alive at their last follow up.

Late effects from ^{131}I -omburtamab are rare except for hypothyroidism related to ^{131}I -uptake and irradiation, which is easily treated with thyroid replacement therapy. Based on the information above, ^{131}I -omburtamab will be further investigated in the proposed phase 2/3 trial for treatment of pediatric NB patients with CNS/ LM metastases.

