9.1.2.7 ***Anti-Drug-Antibody effects on PK and Safety.***

The ADA characterization will deliver occurrence rate of neutralizing antibodies in blood and cerebrospinal fluid (CSF) of exposed patients. Potential associated effects of any neutralizing ADA's on ^{131}I -omburtamab pharmacokinetics (PK) in blood and CSF and safety will be investigated.

9.1.2.7.1 *ADA effects on PK*

Radioactivity counts in blood and CSF will be measured at the following time points after treatment with ^{131}I -omburtamab:

- 1h after treatment
- 6h after treatment
- 24 after treatment
- 7 days after treatment.

The analysis will comprise an intra-patient comparison of PK parameters from the two dose administrations in patients with and without presence of neutralizing ADAs in blood or CSF.

9.1.2.7.2 *ADA effects on Safety*

The analysis will comprise a comparison of reported safety events after the second dose administration in patients with and without presence of neutralizing ADAs in blood or CSF.

9.2 **Other assessments**

9.2.1 **Hematology and clinical chemistry**

Hematology and clinical chemistry will be measured by a local laboratory during screening and in all following treatment cycles and will assess liver and kidney function (ALT, AST, alkaline phosphatase, albumin, bilirubin, BUN, glucose and creatinine), total protein and serum electrolytes (sodium, potassium, chloride and bicarbonate). Complete differential blood count, including eosinophils and platelets, will be performed during screening and in the cycles up to the follow-up at week 26. Thyroid stimulating hormone (TSH)/ free and total T4 to be assessed at screening, pre-dose week 1 and 4, pre-dose week 5 and 8, week 26 if applicable and weeks 52, 78, 104 130 and 156..

If abnormal serum glucose (CTCAE \geq Grade 2) is obtained, a fasting serum glucose is to be obtained at next patient visit. AE reporting of hyperglycemia will require fasting values to assess CTCAE grading.

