9.2.7 Concomitant medication

A concomitant medication is any medication other than the IMP. All concomitant medications must be recorded in the eCRF with the following information:

- Start date
- Stop date of administration or ongoing at trial termination
- Indication/ reason for use
- Dose
- Frequency
- Outcome (for anti-cancer treatments)

Any changes to concomitant medication during the trial will be recorded in the eCRF. All doses of allowed pain relief medication should be recorded as concomitant medication in the eCRF.

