10.7 Expected side-effects related to ^{131}I -omburtamab and dexamethasone

^{131}I -omburtamab:

For detailed description, please refer to current IB.

The risks of ^{131}I -omburtamab include thyroid suppression, neutropenia and myelosuppression requiring red blood cell and/or platelet transfusions. Expected toxicities in the acute phase include the known risks associated with intraventricular infusions: headache, vomiting, and fever in the first few hours post-infusion.

Dexamethasone:

The expected toxicities of dexamethasone include lymphopenia, anemia and hyperglycemia.

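### Late non-serious hypothyroidism, the one late effect the protocol singles out, has no route into the adverse event tables, and the rules for recording thyroid replacement conflict

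*Combined protocol and SAP*

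**What the plan says.** - **The risk.** Section 4.1 states that late effects "are rare except for hypothyroidism related to" uptake of the isotope and irradiation, "which is easily treated with thyroid replacement therapy". Section 10.7 says that the risks of the product "include thyroid suppression, neutropenia and myelosuppression requiring red blood cell and/or platelet transfusions".
- **The measurement.** Table 1 footnote 3 and section 9.2.1 schedule TSH and free and total T4 at screening, weeks 1, 4, 5 and 8, then "week 26 if applicable and weeks 52, 78, 104 130 and 156".
- **The adverse event window.** Table 1 footnote 18: "AEs should be reported until 3 weeks after the last IMP administration". From week 4 (one cycle) or week 8 (two cycles), only serious events considered related, "or new onset of cancers regardless of causality should be reported". Section 10.8 gives the same rule for later serious events, and section 10.9 ends follow-up of non-serious events at 3 weeks after the last dose. The events of special interest in section 10.4 include nothing on the thyroid.
- **Medication.** At week 26 and weeks 52 to 156, footnote 19 says "Limit to therapy related to cancer". Section 9.2.7 requires all concomitant medication and adds: "Any changes to concomitant medication during the trial will be recorded in the eCRF". Section 7.3.1 asks for detailed eCRF capture of treatments given after the study drug, with no restriction to cancer therapy.
- **The analysis.** Section 12.4 tabulates treatment-emergent events from the first dose, with no end date. It also looks at chemistry changes to the end of the trial and at shifts from normal to abnormal in key laboratory parameters, which it does not list.

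**The concern.** The protocol expects this toxicity and measures the hormones for three years, so it plainly wants a conclusion on it. The recording rules work against that. Hypothyroidism that needs replacement meets the protocol's own definition of an adverse event (section 10.1.1: a laboratory abnormality severe enough to need active management). A condition described as easily treated will usually be non-serious, so if it appears after the window it is not reported. The tables in section 12.4 cannot count what was not recorded.

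The medication record would be the natural second source, but the protocol gives sites conflicting instructions on it. Section 6.3 also lets follow-up data come from referral hospitals that are not trained in the protocol, so uneven recording is likely. At stake is the safety statement on the main late toxicity the sponsor already knows about, with an error that runs towards too few cases.

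**Working it through.** No sample size, power or error rate is involved, so there is no plan figure to reproduce. The check is calendar arithmetic followed by a comparison of sections.

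**1. When the window closes.** Inputs: dose on day 1 of each 4-week cycle (section 7.1.1), so days 1 and 29; cycle 2 may be delayed by up to 8 weeks (section 6.1.4); window of 3 weeks = 21 days (footnote 18); follow-up of 156 weeks = 1092 days (Table 1).

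| Case | Last dose | Window closes | Days open after dose 1 | Share of 1092 days |
|---|---|---|---|---|
| One cycle | day 1 | 1 + 21 = day 22 (week 4) | 21 | 1.9% |
| Two cycles | day 29 | 29 + 21 = day 50 (week 8) | 49 | 4.5% |
| Cycle 2 delayed 8 weeks | 29 + 56 = day 85 | 85 + 21 = day 106 (week 16) | 105 | 9.6% |

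Each closes before the week 26 visit, whose own window is 24 to 29 weeks. Re-treatment after relapse (section 6.1.4) would presumably reopen the window for the children concerned.

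**2. Which hormone draws fall outside.** The scheduled post-dose draws are weeks 4, 5, 8, 26, 52, 78, 104, 130 and 156: nine. Those from week 26 on, six of nine, fall after closure. The gaps are 26 − 8 = 18 weeks, then 26 weeks each.

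**3. What the early draws coincide with.** Thyroid blocking runs from 1 week before to 2 weeks after each infusion (section 7.2.5). For cycle 2 that is day 29 − 7 = 22 to day 29 + 14 = 43. The pre-dose week 1 and week 5 draws lie inside a blocking course. Week 4 (days 22 to 28) coincides with the start of the second course. Week 8 (days 50 to 56) comes 7 to 13 days after it ends. The documents do not say how these values are to be read.

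**4. What happens to a late case.**

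| Late case | Adverse event tables | Laboratory shifts | Medication record |
|---|---|---|---|
| Serious and judged related | Yes | Possible | Depends on section followed |
| Non-serious, untreated at a draw | No | Visible if TSH/T4 count as key | Not applicable |
| Non-serious, replacement started between draws | No | May be missed | None under footnote 19; yes under 9.2.7 or 7.3.1 |
| Abnormal at one draw, on replacement by the next | No | Visible once; later values ambiguous | As above |

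In the last two rows, without a treatment record, recovery and continuing replacement cannot be told apart.

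**5. Illustration only.** The documents give no incidence. Assume a 3-year incidence p of 5% to 30%, onset uniform over 156 weeks, 32 children, two cycles and no deaths. Expected cases are 32p = 1.6 to 9.6. Expected cases with onset inside the window are 32p × 49/1092 = 0.07 to 0.43. The chance that at least one arises in the window is 1 − (1 − p × 49/1092)^32 = 7% to 35%. These figures show direction and are not an estimate: onset need not be uniform, and section 4.1 itself reports an estimated 3-year survival of 56% in the preceding trial.

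**The case against.** A time-limited window for non-serious events is a declared design choice, and the protocol has other routes.

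- **Serious cases.** Related serious events remain reportable throughout follow-up, including those judged medically important. This stands: reporting does not stop altogether.
- **Laboratory data.** TSH and T4 belong to the chemistry panel (section 11.1), section 12.4 follows chemistry to the end of the trial, and secondary endpoint 7 covers clinically significant laboratory abnormalities. This stands for children untreated at a draw. It does not help a child whose replacement starts between draws, and the key parameters are not named.
- **General wording.** Section 10.8 opens by asking for every event that meets the definition, and Table 1 ticks adverse events to week 156. Footnote 18 qualifies that same row explicitly, so this does not reopen the window.
- **Medication.** Sections 9.2.7 and 7.3.1 would capture replacement. This stands to the extent that the finding is a contradiction to reconcile. A reader might infer that replacement is definitely not recorded; the documents do not settle that.

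Two further inferences go too far. One is that treated children will be counted as having normal thyroid function. That they may have normal values is reasonable, but the documents say only that the condition is easily treated. They do not say how values on replacement are classified, and section 12.1 leaves data handling to the SAP, of which no separate text was available to check. The other is that the trial would misjudge whether thyroid blocking works: that is neither an objective nor an endpoint, and a single-arm trial could not answer it.

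**Conclusion.** The concern holds in a limited form. Hypothyroidism that is non-serious and arises after day 22, 50 or 106, depending on the cycles given, has no route into the adverse event tables. The instructions on recording its treatment disagree. If footnote 19 is followed, some children who start replacement between draws 18 to 26 weeks apart may be missed, and later TSH/T4 values cannot be interpreted.

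The likely direction is under-reporting, but the size cannot be derived: the documents give no incidence, no onset distribution and no rule for values on treatment. A reader might expect the tables to show no cases at all. That would require every case to be non-serious and to start after the window, which nothing in the documents establishes. The conclusion rests on footnote 18 being applied as written and on most cases being non-serious, which section 4.1 suggests but does not state.

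**What to change.** These changes concern data capture and analysis only.

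1. **Footnote 19 with sections 7.3.1 and 9.2.7.** Reconcile them so that start and stop dates of thyroid hormone replacement are recorded to week 156.
2. **Footnote 18 with sections 10.8 and 10.9.** Add an exception: newly diagnosed hypothyroidism, with onset date and grade, is recorded to week 156 whether or not it is serious.
3. **Section 12.4.** Name TSH and T4 as key laboratory parameters. Report the proportion of children with abnormal TSH/T4 at week 26 or later, or with new thyroid replacement after the first dose other than the protocol's blocking course. Present values drawn during or shortly after blocking separately, so that they do not define cases.

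The cost is a few text edits, one eCRF field at existing visits, one analysis definition and a few more adverse event entries. The thyroid figure may look less favourable. No visit, test or treatment rule changes.

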4 INTRODUCTION

4.1 Medical background

NB is a rare cancer of neural crest origin. The neuroectodermal cells that comprise neuroblastic tumors originate from the neural crest during fetal development and are destined for the adrenal medulla and sympathetic nervous system. Neuroblasts can transform into NB, a term that may be used to describe a spectrum of neuroblastic tumors, including ganglioneuroma (benign), NB (malignant), and ganglioneuroblastoma (borderline aggressive). In this text, NB refers to the malignant form if not specified otherwise. NB is a disease of childhood. About 37% of patients are diagnosed as infants, and 90% are younger than 5 years, with a median age of 19 months, at diagnosis (London et al. 2005). The highest incidence is seen in the first months of life (Howlader et al. 2012; Gurney et al. 1997; London et al. 2005).

NB is a life-threatening disease that is associated with poor long-term survival. Generally, survival rates depend highly on whether the tumor is low risk, intermediate risk, or high risk:

- For patients with low-risk tumors, five-year OS was 97% in a large COG trial (Strother et al. 2012).
- For patients with intermediate-risk tumors, three-year OS rate was about 96% in a large COG trial (Baker et al. 2010).
- For high-risk patients, survival rates of 40-50% have not changed significantly during the last two decades (Pinto et al. 2015).

Conventional systemic treatment for newly diagnosed patients does not adequately treat the central nervous system and leptomeningeal (LM) space, which may serve as a sanctuary site leading to relapse (Matthay et al. 2003; Kramer, Gerald, et al. 2001). In large series, the incidence of CNS/LM disease in relapsed patients is between 6-10% and the incidence of CNS/LM tumor will likely increase as better treatment options induce longer systemic remissions and increased frequency of CNS relapse. CNS relapses are almost uniformly lethal (Matthay et al. 2003; Choi et al. 2005; Zhu et al. 2015; Kellie et al. 1991; Shaw and Eden 1992; Wiens and Hattab 2014; Watts 1992; Sakata et al. 1993; Astigarraga et al. 1996; Kramer, Kushner, et al. 2001). Specific factors that can predict CNS/LM metastasis have not been identified.

Furthermore, general management guidelines for recurrent NB in CNS are lacking consensus in Europe and the US, and specific treatment for metastatic CNS NB has yet to be approved.

Leptomeningeal cancer remains a challenging problem and the long-term outcome for children with leptomeningeal disease due to solid tumors remains poor with rapid progression over a period of weeks to months (Neville KA, Blaney SM. Leptomeningeal cancer in the pediatric patient. *Cancer Treat Res.* 2005; 125:87-106

). In addition, there are significant toxicities associated with therapy in those children who are ultimately cured. Various treatment combinations, comprising one or more of the following treatments, are currently used in the clinic:

- Surgery of bulky tumor prior to irradiation and chemotherapy to reduce symptoms, edema and hemorrhage or to correct CSF flow.
- Craniospinal or focal irradiation to alleviate symptoms and to obtain disease control and to correct CSF flow in case of obstruction.

- Standard systemic combination chemotherapy (e.g., irinotecan plus temozolomide) may improve outcome, but significant toxicity and complications typically limit this form of treatment to patients with high likelihood of benefit.

Memorial Sloan Kettering Cancer Center (MSK) has developed ^{131}I -omburtamab for the treatment of pediatric recurrent NB with CNS/LM metastases and ^{131}I -omburtamab has been studied in █ clinical trials at MSK with more than █ treated patients over 15 years. ^{131}I -omburtamab has been used as monotherapy for the treatment of NB patients with CNS/LM metastases (trial 03-133) and patients with Desmoplastic Small Round Cell Tumor (DSRCT) (trial 09-090). In addition, ^{131}I -omburtamab has been used in a tumor detection trial (trial 00-066).

The development of ^{131}I -omburtamab for the treatment of NB with CNS/LM metastases has entered phase 1/2, and an interim analysis (data reported through Aug-2017) based on █ from the on-going trial 03-133 is available. The results hold promise for a potential breakthrough as evidenced by low toxicity, high rate of radiographic improvements, and long-term survival.

The median survival for the patients included in the interim analysis was 47 months versus 6 months in various historical cohorts (Kramer, Kushner, and Modak 2017; Berthold, Hömberg, and Baadsgaard 2017). Survival past 3 years historically is rare, less than 10% (Kramer et al. 2017), which is aligned with findings by (Berthold, Hömberg, and Baadsgaard 2017), demonstrating a 3-year survival rate of 8.2% (Berthold et al. 2017). In contrast, for NB patients in study 03-133, the estimated 3-year survival of 56% and an estimated 5-year survival of 43% is reported. Survivors have been followed for up to 11.1 years, with a current mean duration of follow up of 2.6 years. Fifty-one (54.8%) of the █ patients treated with ^{131}I -omburtamab remained alive at their last follow up.

Late effects from ^{131}I -omburtamab are rare except for hypothyroidism related to ^{131}I -uptake and irradiation, which is easily treated with thyroid replacement therapy. Based on the information above, ^{131}I -omburtamab will be further investigated in the proposed phase 2/3 trial for treatment of pediatric NB patients with CNS/ LM metastases.

4.2 Drug profile

4.2.1 ^{131}I -omburtamab

^{131}I -omburtamab is a radiolabeled monoclonal antibody that targets cluster of differentiation 276 (CD276) (also known as B7-H3, (Modak, 2001 #471)(Xu et al. 2009). CD276 is a member of the B7/CD28 immunoglobulin superfamily which regulates T-cell functions in tumor surveillance, infections, and autoimmune diseases. CD276 is a tumor-associated antigen highly overexpressed on a wide range of human solid tumors, but minimally in normal tissues. CD276 is distributed on the cell membrane of solid tumors of neuroectodermal, mesenchymal, and epithelial origin in adult and pediatric patients and its presence is often correlated with negative prognosis and poor clinical outcome. Upon administration, ^{131}I -omburtamab binds selectively to the B7-H3 antigen (CD276/B7-H3) expressed on tumor cell membranes. The iodine-131 emits beta radiation that causes deoxyribonucleic acid (DNA) damage and tumor cell death. Iodine-131 has a half-life of 8 days and the beta radiation penetrates up to 3 millimeters, with effects

not only on the antibody binding cell, but also on neighboring tumor cells (Larson et al. 2015). For further information, please see the current ^{131}I -omburtamab Investigator's Brochure (IB).

4.2.1.1 ***Non-clinical pharmacology and toxicology***

Pharmacology

[REDACTED]

Toxicology

[REDACTED]

An overview of the studies is presented in the IB.

Non-clinical summary

[figure not shown]
[REDACTED]

4.2.1.2 ***Effects on Humans***

Normal Organ Dosimetry

[figure not shown]
[REDACTED]

from an interim analysis of dosimetry show that absorbed dose estimates exhibit high inter-patient variability across all organs, consistent with previous results from previous trials with ^{131}I -omburtamab (Table 2). For more detailed information, please see the current ^{131}I -omburtamab investigator's brochure.

Previous clinical experience

To date the MSK-produced ^{131}I -omburtamab has been used in █ clinical trials at MSK, U.S.

4.2.2 Radiolabeling

Omburtamab will be radiolabeled with iodine-131 by a radiopharmacy connected to the treating institution or at a designated central radiopharmacy (section 7.1) according to a qualified procedure described in a manufacturing agreement.

